## 11.2. Data Analysis Populations

The Per-Protocol (PP) efficacy analysis population includes all randomized subjects who met all inclusion/exclusion criteria, did not have any significant protocol deviations, complied with the assigned study treatment, returned to the study site for the Test of Cure visit within the specified window (Visit 2 Study Day 8 relative to the first day of treatment [Window: Days 8-15]), or discontinued study product early due to lack of treatment effect or received vaginosis or systemic antimicrobial therapy other than study drug during the study. Subjects with Visit 1 test results including a grade 3 laboratory abnormality, a positive Visit 1 HIV, *Chlamydia*, or *Neisseria gonorrhoeae* test, a PAP result consistent with HSIL, AGUS, or CIN2 or greater, or a Visit 1 Nugent score < 4 will excluded from the PP population.

A subject is compliant with study treatment if she uses at least 5 of 6 doses of study product, as assessed by the study coordinator's count of used / unused applicators in each returned subject kit. If a kit is not returned, compliance will be assessed by the subject's self-report on the memory aid. Significant protocol deviations include sexual intercourse including receptive oral sex or insertion of substances or objects intravaginally between Visit 1 and Visit 2.

The Modified Intent-to-Treat (mITT) efficacy analysis population includes all randomized subjects who met all inclusion/exclusion criteria excluding those who have a Nugent score <4 at Visit 1 or are positive for other concomitant vulvovaginal infections at baseline which may interfere with the efficacy assessment. The mITT population will be used as the primary analysis population for the test of 5% Monolaurin Vaginal Gel to Vehicle Placebo Gel.

The Evaluable efficacy analysis population includes all subjects in the mITT population who received study treatment and returned for at least one post-baseline visit.

The Intent-to-Treat (ITT) efficacy analysis population includes all randomized subjects.

The safety population includes all randomized subjects who received at least one dose of study product.

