6.3.5. Per Protocol Population

The Per Protocol (PP) population for all endpoints measured at Visit 2 includes all randomized subjects who met all inclusion/exclusion criteria, did not have sexual intercourse including receptive oral sex or insertion of substances or objects intravaginally between Visit 1 and Visit 2, complied with the assigned study treatment, returned to the study site for the Test of Cure visit within the specified window (Visit 2 Study Day 8 relative to the first day of treatment [Window: Days 8-15]), or discontinued study product early due to lack of treatment effect or received vaginosis or systemic antimicrobial therapy other than study drug before Visit 2. Subjects with

Visit 1 test results including a grade 3 laboratory abnormality, a positive Visit 1 HIV, Chlamydia, or *Neisseria gonorrhoeae* test, are found to have a PAP result consistent with HSIL, AGUS, or CIN2 or greater, or a Visit 1 Nugent score < 4 will be excluded from the PP population. A review of medical history and concomitant medications will be performed to identify any other infections that may interfere with the efficacy assessment. Subjects with these identified infections will be excluded from the PP population.

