The PP population for all endpoints measured at Visit 3 includes all randomized subjects who met all inclusion/exclusion criteria, did not have sexual intercourse including receptive oral sex or insertion of substances or objects intravaginally between Visit 1 and Visit 2 or 48 hours before Visit 3, complied with the assigned study treatment, returned to the study site for Visit 2 and Visit 3 within the specified windows (Visit 2 Study Day 8 relative to the first day of treatment [Window: Days 8-15]), Visit 3 Study Day 28 relative to the first day of treatment [Window: Days 8-15]), or discontinued study product early due to lack of treatment effect or received vaginosis or systemic antimicrobial therapy other than study drug between Visits 1 and 3. Subjects with Visit 1 test results including a grade 3 laboratory abnormality, a positive Visit 1 HIV, Chlamydia, or Neisseria gonorrhoeae test, are found to have a PAP result consistent with HSIL, AGUS, or CIN2 or greater, or a Visit 1 Nugent score < 4 will be excluded from the PP population. A review of medical history and concomitant medications will be performed to identify any other infections that may interfere with the efficacy assessment. Subjects with these identified infections will be excluded from the PP population.

See Section 9.2 for measurements of compliance.

In the unlikely event of an error in randomization or study product administration (i.e., incorrect product), subjects will be grouped by the product they actually received.

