	Evaluable	Positive for other concomitant vulvovaginal infections		X	х	х	х	Х
		Did not receive study product		x	х	х	х	х
		Did not return for at least one post- baseline visit		X	X	х	х	Х
	Eligible for PP		х	х	х	х	х	х
		Any Reason	х	х	х	х	х	х
Evaluable Analysis Population Per-Protocol (PP) Analysis Population		Did not meet inclusion/exclusion criteria	x	x	х	х	х	х
		Had significant protocol deviations	х	x	x	х	х	х
		Received less than 5 doses of study product	х	х	х	х	х	х
		Did Not Return for Test of Cure visit	х	х	х	х	х	х
		Out of window Test of Cure visit	x	х	х	x	х	х
Per-Protocol (PP) Analysis		Discontinued early due to lack of treatment effect	х	х	x	х	х	х
Population	Excluded from PP	Received systemic antimicrobial therapy other than study drug	х	х	х	x	х	х
		Grade 3 Lab Abnormality from Visit 1	x	х	х	х	х	х
		Positive HIV, Chlamydia or Neisseria gonorrhoeae test	х	X	X	х	х	Х
		Positive for other concomitant vulvovaginal infections	X	X	х	Х	х	Х
		PAP result consistent with HSIL, AGUS, or CIN2 or greater	X	X	X	X	X	Х
		Nugent score < 4 from Visit 1	x	x	X	x	x	х

Table 4:Safety, Evaluable, and Per-Protocol Analysis Populations by
Treatment Group

Note: N=number of enrolled subjects; Treatment group is the actual treatment a subject received

Subject	5% Monol (I	aurin Vaginal Gel N=X)	Place (N	bo Gel =X)	All Subjects (N=X)			
Disposition	Ν	%	n	%	n	%		
Screened					Х			
Enrolled/Randomized	х	100	Х	100	Х	100		
Received Treatment	х	X	Х	х	Х	х		
Complied with Treatment ^{a, b}	х	х	х	х	х	х		
Completed Test of Cure Visit, Visit 2 (Study Day 8-15)	х	X	х	X	Х	Х		
Completed Test of Cure Visit Per Protocol ^c	х	Х	Х	х	Х	Х		
Completed Visit 3 (Study Day 22- 31)	х	Х	Х	Х	Х	Х		
Completed Visit 3 Per Protocol ^c	х	Х	Х	х	Х	х		

Subject Disposition by Treatment Group - All Enrolled Subjects Table 5:

Notes: N=Number of enrolled subjects ^aRefer to Listing 1 (16.2.1) for reasons subjects discontinued or terminated early.

^b Refer to Listing 9 (16.2.5) for treatment compliance. ^cRefer to Listing 4 (16.2.3) for reasons subjects are excluded from the per protocol population.

	5% Monol Vaginal (N=X			aurin Gel	Placebo Gel (N=X)			All	All Subjects (N=X)		
Category	Deviation Type	# of Subj.	%	# of Dev.	# of Subj.	%	# of Dev.	# of Subj.	%	# of Dev.	
Eligibility/enrollment	Any type	х	х	х	х	х	х	х	х	х	
	Did not meet inclusion criterion	х	х	х	х	х	х	х	x	х	
	Met exclusion criterion	х	х	х	х	x	х	х	x	х	
	ICF not signed prior to study procedures	х	x	х	х	x	х	х	x	х	
	Other	х	x	х	х	x	х	х	x	х	

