Site	Deviation	Start Day	End Day	Reason for Deviation	Deviation Resulted in Subject Termination?	Deviation Affected Product Stability?	Deviation Category	Deviation Resolution	Comments
xxxx	XXXX	XX	XX	xxxx	Yes/No	Yes/No/NA	XXXX	xxxx	XXXX
XXXX	XXXX	XX	XX	XXXX	Yes/No	Yes/No/NA	XXXX	XXXX	XXXX

Note: Deviation column will contain all subfields concatenated together

Implementation Notes:

1. Sort order will be by Site Name, Start Date

2. In the Deviation Category column concatenate any specify fields

3. In the Reason for Deviation column concatenate any specify fields.

Randomized Treatment Group	Actual Treatment Group	Subject ID	Analyses in which Subject is Included	Analyses from which Subject is Excluded	Results Available?	Reason(s) Subject Excluded
5% Monolaurin Vaginal Gel/Placebo Gel	5% Monolaurin Vaginal Gel/Placebo Gel	xxxxx	[e.g., Safety, ITT, mITT, Evaluable, PP]	[e.g., Safety, ITT, mITT, Evaluable, PP, Visit x]	Yes/No	XXXXX
5% Monolaurin Vaginal Gel/Placebo Gel	5% Monolaurin Vaginal Gel/Placebo Gel	xxxxx	[e.g., Safety, ITT, mITT, Evaluable, PP]	[e.g., Safety, ITT, mITT, Evaluable, PP, Visit x]	Yes/No	XXXXX
5% Monolaurin Vaginal Gel/Placebo Gel	5% Monolaurin Vaginal Gel/Placebo Gel	xxxxx	[e.g., Safety, ITT, mITT, Evaluable, PP]	[e.g., Safety, ITT, mITT, Evaluable, PP, Visit x]	Yes/No	XXXXX

Listing 4: 16.2.3 Subjects Excluded from Analysis Populat

Note: "Yes" in the "Results available" column indicates that available data were removed from the analysis. If "Yes" the population in which data were removed will be listed in parenthesis. "No" indicates that no data were available for inclusion in the analysis.

Implementation Notes:

1. Sort order will be randomized treatment group, Subject ID

2. Reasons Subject Excluded should match the same verbiage that is used on the Analysis population tables (Tables 3 and 4)

3. For subjects excluded from the Per Protocol population, specify which visit's PP population (Visit 2 or Visit 3) the subject is excluded from

Listing 5:	16.2.4.1 Demographics Data -	All Enrolled Subjects
------------	------------------------------	-----------------------

Subject ID	Randomized Treatment Group	Actual Treatment Group	Age at Enrollment (years)	Ethnicity	Race
XXXXXX	5% Monolaurin Vaginal Gel/Placebo Gel	5% Monolaurin Vaginal Gel/Placebo Gel	XX	XXXXXX	XXXXXX
XXXXXX	5% Monolaurin Vaginal Gel/Placebo Gel	5% Monolaurin Vaginal Gel/Placebo Gel	XX	XXXXXX	XXXXXX

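### SAP Table 4 excludes from the per-protocol set treatment failures that SAP 6.3.5 includes, and the Visit 3 per-protocol window is given as Days 8-15 instead of Days 22-31

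*SAP*

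**What the plan says.** SAP 6.3.5 defines the Visit 2 PP set by eligibility, abstinence, compliance and an in-window Test of Cure visit, and then adds an alternative: "or discontinued study product early due to lack of treatment effect or received vaginosis or systemic antimicrobial therapy other than study drug before Visit 2". The Visit 3 PP set repeats the branch for women who "received vaginosis or systemic antimicrobial therapy other than study drug between Visits 1 and 3". Protocol 11.2 has it too: "discontinued study product early due to lack of treatment effect or received vaginosis or systemic antimicrobial therapy other than study drug during the study". SAP 3.3.3 makes both events clinical failures.

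The Table 4 shell in SAP Appendix I has a block of reasons for exclusion from PP. Two of its rows are "Discontinued early due to lack of treatment effect" and "Received systemic antimicrobial therapy other than study drug". Listing 4 carries the instruction "Reasons Subject Excluded should match the same verbiage that is used on the Analysis population tables (Tables 3 and 4", and Table 5 sends the reader to Listing 4 for PP exclusions.

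The Visit 3 PP paragraph describes the visit as "Visit 3 Study Day 28 relative to the first day of treatment [Window: Days 8-15". Protocol 7.3, the schedules of events and SAP 3.2.2 all give Days 22-31 for Visit 3. SAP 6.2 gives Days 22-30.

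**The concern.** The same women are inside the PP set by its definition and outside it by the table that reports it. The SAP does not say which prevails, and SAP section 12 declares no change here. Because these women are failures, removing them makes PP membership depend on outcome.

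At Visit 3 the literal window admits nobody who attended on schedule. PP is a prespecified repeat of the primary test at Visit 2, with its own p-value in Table 29, and it supplies the PP rows for Visit 3 cure in Tables 30 and 32. If the conflict is left until treatment codes are open, resolving it becomes a choice made with knowledge of the results.

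**Working it through.** **Text comparison**

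| Item | SAP 6.3.5 | SAP Table 4, PP block |
|---|---|---|
| Early stop for lack of effect | Included through the alternative branch | Reason for exclusion |
| Other systemic antimicrobial | Included through the branch | Reason for exclusion |
| Other vaginosis therapy | Included through the branch | Not named |
| Fewer than 5 doses | Compliance required; relation to the branch not stated | Reason for exclusion |
| No Test of Cure visit, or out of window | The branch is an alternative to the visit | Reason for exclusion |
| Separate Visit 3 PP set | Defined | No rows |

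SAP 6.5 removes women who are not evaluable at Test of Cure from PP. That does not resolve the conflict, because a woman meeting a failure criterion is evaluable.

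The compliance row matters in its own right. SAP 3.3.9 requires at least 5 of 6 doses. A woman who stops a six-dose course early will often fall short, so deleting the two contested rows would not by itself keep her in the set.

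**Visit 3 window.** Days 8-15 and Days 22-31 share no day, and Day 28 is not in Days 8-15. Read literally, only the branch can supply members. All of them are failures, so the cure rate would be 0% in both arms.

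**Size at Visit 2.** The plan gives no figure to reproduce and no rate for these failures, so this is an illustration. The arm sizes of 60 and 30 are the planning sizes in SAP section 5. Cure of 50% (30 women) and 20% (6 women) is assumed. With c cures, n women and d failures dropped, the PP rate is c/n under 6.3.5 and c/(n − d) under Table 4. P-values are two-sided Fisher's exact.

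| Dropped, active / placebo | Active | Placebo | Difference (points) | p |
|---|---|---|---|---|
| 0 / 0 | 30/60 = 50.0% | 6/30 = 20.0% | 30.0 | 0.0067 |
| 6 / 3 (10% each) | 30/54 = 55.6% | 6/27 = 22.2% | 33.3 | 0.0049 |
| 12 / 6 (20% each) | 30/48 = 62.5% | 6/24 = 25.0% | 37.5 | 0.0054 |
| 3 / 6 (5%, 20%) | 30/57 = 52.6% | 6/24 = 25.0% | 27.6 | 0.028 |

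With no true difference (18/60 and 9/30, both 30%), dropping 10% of active and 30% of placebo gives 18/54 = 33.3% and 9/21 = 42.9%, a difference of −9.5 points. Dropping 10% in each arm leaves 33.3% in both.

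**Size at Visit 3 if the same rows were applied there.** Keep 50% and 20% at Visit 2 and assume 80% of cures last. Sustained cures are 60 × 0.50 × 0.80 = 24 and 30 × 0.20 × 0.80 = 4.8. Visit 2 failures number 30 and 24. If a fraction f of those failures is dropped, the rates are 24/(60 − 30f) and 4.8/(30 − 24f).

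| f | Active | Placebo | Difference (points) |
|---|---|---|---|
| 0 | 0.400 | 0.160 | 24.0 |
| 0.25 | 0.457 | 0.200 | 25.7 |
| 0.50 | 0.533 | 0.267 | 26.7 |
| 0.75 | 0.640 | 0.400 | 24.0 |
| 0.90 | 0.727 | 0.571 | 15.6 |
| 1.00 | 0.800 | 0.800 | 0 |

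Both rates rise throughout. The difference stays within 3 points of 24 up to f = 0.75 and falls to zero only as f approaches 1.

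**The case against.** The strongest reply is that 6.3.5 defines the population, while Table 4 is an example shell that counts reasons, and Listing 4 asks only for matching wording. If the programmers work from 6.3.5, the Visit 2 PP cure rates are right and two rows of a disposition table are mislabelled or print zero. That stands. A reader might infer that the PP results will be wrong. The documents support only the conditional: they go wrong if Table 4 or the literal window is what gets programmed.

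The Days 8-15 window is very likely a copying error, since the same clause says Day 28. That also stands, so 0% cure in both arms is the literal reading and not a forecast. The intended end of the window still needs stating, because SAP 6.2 differs by a day from the other places.

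A reader might also infer that Table 4 would erase a Visit 3 treatment difference. That needs every Visit 2 failure to receive systemic therapy. Protocol 7.2 makes referral depend on the investigator's judgement, and two of the three first-line regimens listed in protocol 2.1 are intravaginal. The Table 4 row names systemic antimicrobials only, and its visit rows concern Test of Cure. The collapse to zero is one end of the range above.

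Finally, counting systemic antimicrobials as failure is an SAP rule. Protocol 11.3 names only vaginosis therapy. The statement that both groups are failures therefore rests on SAP 3.3.3.

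**Conclusion.** Both contradictions are in the current text and concern the rules for a prespecified analysis set. The primary mITT comparison does not depend on them; PP is a secondary analysis. If Table 4 were followed, both arms' PP cure rates would be inflated and the difference could move either way. Under the assumed 50% and 20% at Visit 2, with 5% to 20% of an arm dropped, 30 points becomes about 28 to 38. Those cure rates and dropped fractions are assumptions, and the documents give nothing from which to estimate them. A stronger conclusion, that the trial's efficacy finding is at risk or that a Visit 3 difference would vanish, is not supported. The point is worth fixing because membership of the set has opposite answers at Visit 2 and an unusable literal definition at Visit 3.

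**What to change.** 1. Remove the two rows from the Table 4 exclusion reasons, or show these women as included clinical failures, and align Listing 4.
2. Rewrite 6.3.5 with explicit grouping. A woman who stops early for lack of effect, or receives other therapy before the visit concerned, is included as a failure whatever her visit timing and dose count. The Table 4 rows for too few doses, no return and out-of-window return should not be applied to her. Bracketing the branch only against the visit window would leave early discontinuers excluded by the 5-of-6-dose rule.
3. Name vaginosis therapy alongside systemic antimicrobials wherever the branch is reported, and reconcile SAP 3.3.3 with protocol 11.3 on systemic antimicrobials.
4. Correct the Visit 3 PP window to Days 22-31 and reconcile Days 22-30 in SAP 6.2.
5. Split the Table 4 PP block into Visit 2 and Visit 3. Listing 4 already asks for PP exclusions by visit.

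The cost is edits to SAP text and shells before database lock. No new data, procedures or sample size are needed.

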#### 11.7.2. Efficacy Analyses

#### 11.7.2.1. Overview of Efficacy Analyses

#### 11.7.2.1.1. Analyses of Primary and Secondary Efficacy Outcomes

• Primary Efficacy Outcome – the proportion of subjects with clinical cure in each study arm at Visit 2 (Day 8-15).

A test of hypothesis for the primary efficacy outcome will be conducted in the mITT efficacy analysis population, and repeated as a secondary analysis in the PP efficacy analysis population, Evaluable efficacy analysis population, and Intent-to-Treat efficacy analysis population. Fisher's exact test at the 5% two-sided level of significance level will be used without adjustment for multiplicity. The point estimates for the arm-specific proportions and difference in proportions as well as corresponding 95% confidence intervals will be reported.

- Secondary Efficacy Outcomes
  - Proportion of subjects with therapeutic cure in each study arm at Visit 2 (Day 8-15) and at Visit 3 (Day 22-31).
  - Proportion of subjects with clinical cure in each study arm by Visit 3 (Day 22-31)
  - Proportion of subjects with Nugent score of 3 or less (negative for BV) and 4-6 (intermediate) in each study arm at Visit 2 (Day 8-15) and at Visit 3 (Day 22-31)

The analyses of the secondary efficacy outcomes will be conducted in the mITT efficacy analysis population and repeated in the PP efficacy analysis population, Evaluable efficacy analysis population and Intent-to-Treat efficacy analysis population. The point estimates for the armspecific proportions and difference in proportions as well as corresponding 95% confidence intervals will be reported.

Additional descriptive analyses of the primary and secondary efficacy outcomes will be performed including tabular and graphical displays of the data, reporting outcomes overall and separately by treatment arm.

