8.2. Secondary Efficacy Analyses

Secondary efficacy analyses will be performed in the mITT, ITT, Evaluable and PP populations. The mITT and ITT populations will be summarized by randomized treatment and the Evaluable and PP populations will be summarized by actual treatment received.

Table 30 presents the proportion of subjects with clinical cure in each treatment group at Visit 3 (Day 22-31). The number of subjects, the proportion of subjects who achieved clinical cure (clinical cure rate), and the 95% Wilson confidence interval for the proportion of subjects achieving clinical cure will be presented for each analysis population and treatment group. In addition, the difference in proportions between the 5% Monolaurin Vaginal Gel arm and the Placebo gel arm and 95% Wilson confidence intervals will be presented.

Tables 31 and 32 present the proportion of subjects with therapeutic cure in each treatment group at Test of Cure Visit, Visit 2 (Day 8-15) and at Visit 3 (Day 22-31), respectively. The number of subjects, the proportion of subjects who achieved therapeutic cure (therapeutic cure rate), and the 95% Wilson confidence interval for the proportion of subjects achieving therapeutic cure will be presented for each analysis population, treatment group, and study visit. In addition, the difference in proportions between the 5% Monolaurin Vaginal Gel arm and the Placebo gel arm and 95% Wilson confidence intervals will be presented.

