Tables 38-41 presents the number and proportion of subjects with Nugent scores falling in negative BV (3 or less), intermediate (4-6), and BV (7-10) range by analysis population, study visit, and site. The 95% Wilson confidence intervals for the proportion of subjects falling in each category will also be presented. **Tables 42-43** presents the proportion of subjects with Nugent score of 3 or less (negative for BV), 4-6 (intermediate), and 7-10 (positive for BV) in each treatment group at Visit 1, at Visit 2 (Day 8-15) and at Visit 3 (Day 22-31). The number and proportion of subjects with Nugent scores falling in negative, intermediate, and BV range is presented by analysis population, study visit, and treatment group. The 95% Wilson confidence intervals will also be presented. Mean Nugent scores will also be presented by analysis population, study visit, and treatment group in **Table 44.** A subject listing of Nugent scores and bacterial morphotypes will be presented in **Listing 23**. Raw Nugent scores are displayed graphically by visit, treatment group, and analysis population in **Figures 2-5**. Categorical and Continuous Nugent Score characteristics are presented by study visit, clinical cure status, and treatment group for subjects in the ITT population in **Tables 45 and 46**. See Section 6.1 for pseudocode to use in calculating the 95% CIs.

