	All Subjects	х	х	0.xx	0.xx, 0.xx			
	5% Monolaurin Vaginal Gel	Х	х	0.xx	0.xx, 0.xx	0.xx	0.xx, 0.xx	0.xxx
Evaluable	Placebo Gel	Х	х	0.xx	0.xx, 0.xx			
	All Subjects	х	х	0.xx	0.xx, 0.xx			
	5% Monolaurin Vaginal Gel	Х	х	0.xx	0.xx, 0.xx	0.xx	0.xx, 0.xx	0.xxx
PP	Placebo Gel	X	x	0.xx	0.xx, 0.xx			
	All Subjects	X	X	0.xx	0.xx, 0.xx			

Notes: The denominator for proportions is based on the number of subjects enrolled in the respective treatment group and analysis population.

*P-value from the Fisher's exact two-sided test at the .05 level of significance.

Analysis Population	Treatment Group	Number of Subjects with Clinical Cure n	Number of Subjects N	Proportion of Subjects with Clinical Cure	Proportion of Subjects with Clinical Cure 95% CI	Difference in Proportion of Subjects with Clinical Cure between 5% Monolaurin Vaginal Gel and Placebo Gel	Difference in Proportion of Subjects with Clinical Cure between 5% Monolaurin Vaginal Gel and Placebo Gel 95% CI
	5% Monolaurin Vaginal Gel	X	х	0.xx	0.xx, 0.xx	0.xx	0.xx, 0.xx
ITT	Placebo Gel	Х	х	0.xx	0.xx, 0.xx		
	All Subjects	Х	х	0.xx	0.xx, 0.xx		
	5% Monolaurin Vaginal Gel	Х	х	0.xx	0.xx, 0.xx	0.xx	0.xx, 0.xx
mITT	Placebo Gel	х	х	0.xx	0.xx, 0.xx		
	All Subjects	Х	х	0.xx	0.xx, 0.xx		
	5% Monolaurin Vaginal Gel	X	х	0.xx	0.xx, 0.xx	0.xx	0.xx, 0.xx
Evaluable	Placebo Gel	Х	х	0.xx	0.xx, 0.xx		
	All Subjects	х	х	0.xx	0.xx, 0.xx		
	5% Monolaurin Vaginal Gel	х	х	0.xx	0.xx, 0.xx	0.xx	0.xx, 0.xx
PP	Placebo Gel	X	х	0.xx	0.xx, 0.xx		
	All Subjects	X	X	0.xx	0.xx, 0.xx		

Table 30: Clinical Cure Results at Visit 3 by Analysis Population and Treatment Group

Note: The denominator for proportions is based on the number of subjects enrolled in the respective treatment group and analysis population.

Analysis Population	Treatment Group	Number of Subjects with Therapeutic Cure n	Number of Subjects N	Proportion of Subjects with Therapeutic Cure	Proportion of Subjects with Clinical Cure 95% CI	Difference in Proportion of Subjects with Therapeutic Cure between 5% Monolaurin Vaginal Gel and Placebo Gel	Difference in Proportion of Subjects with Therapeutic Cure between 5% Monolaurin Vaginal Gel and Placebo Gel 95% CI
	5% Monolaurin Vaginal Gel	х	x	0.xx	0.xx, 0.xx	0.xx	0.xx, 0.xx
ITT	Placebo Gel	Х	х	0.xx	0.xx, 0.xx		
	All Subjects	Х	х	0.xx	0.xx, 0.xx		
	5% Monolaurin Vaginal Gel	X	х	0.xx	0.xx, 0.xx	0.xx	0.xx, 0.xx
mITT	Placebo Gel	Х	х	0.xx	0.xx, 0.xx		
	All Subjects	Х	х	0.xx	0.xx, 0.xx		

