Note: Denominator for percentages is the number of subjects enrolled (N) in the study for each Site.

- Table 39:
 Nugent Scores by Category, Study Visit, Analysis Population, and Site—Cincinnati Children's Hospital
- Table 40:
 Nugent Scores by Category, Study Visit, Analysis Population, and Site—University of Iowa
- Table 41:
 Nugent Scores by Category, Study Visit, Analysis Population, and Site—Duke University

					5%	Monolaurin Vag (N = X)	ginal Gel			
Analysis	Nugent Score		Visit 1 (N = X)			Visit 2 (N = X)			Visit 3 (N = X)	
Population	Category	Number of Subjects n	Proportion of Subjects	Proportion of Subjects 95% CI	Number of Subjects n	Proportion of Subjects	Proportion of Subjects 95% CI	Number of Subjects n	Proportion of Subjects	Proportion of Subjects 95% CI
	0-3 (Normal)	х	0.xx	0.xx, 0.xx	Х	0.xx	0.xx, 0.xx	х	0.xx	0.xx, 0.xx
ITT	4-6 (Intermediate)	х	0.xx	0.xx, 0.xx	Х	0.xx	0.xx, 0.xx	х	0.xx	0.xx, 0.xx
	7-10 (BV)	X	0.xx	0.xx, 0.xx	Х	0.xx	0.xx, 0.xx	X	0.xx	0.xx, 0.xx
	0-3 (Normal)	X	0.xx	0.xx, 0.xx	Х	0.xx	0.xx, 0.xx	X	0.xx	0.xx, 0.xx
mITT	4-6 (Intermediate)	X	0.xx	0.xx, 0.xx	Х	0.xx	0.xx, 0.xx	X	0.xx	0.xx, 0.xx
	7-10 (BV)	X	0.xx	0.xx, 0.xx	Х	0.xx	0.xx, 0.xx	X	0.xx	0.xx, 0.xx
	0-3 (Normal)	X	0.xx	0.xx, 0.xx	х	0.xx	0.xx, 0.xx	X	0.xx	0.xx, 0.xx
Evaluable	4-6 (Intermediate)	X	0.xx	0.xx, 0.xx	х	0.xx	0.xx, 0.xx	X	0.xx	0.xx, 0.xx
	7-10 (BV)	X	0.xx	0.xx, 0.xx	Х	0.xx	0.xx, 0.xx	X	0.xx	0.xx, 0.xx
	0-3 (Normal)	x	0.xx	0.xx, 0.xx	х	0.xx	0.xx, 0.xx	x	0.xx	0.xx, 0.xx
PP	4-6 (Intermediate)	X	0.xx	0.xx, 0.xx	х	0.xx	0.xx, 0.xx	X	0.xx	0.xx, 0.xx
	7-10 (BV)	X	0.xx	0.xx, 0.xx	Х	0.xx	0.xx, 0.xx	X	0.xx	0.xx, 0.xx

Table 42:Nugent Scores by Category, Study Visit, Analysis Population, and Treatment Group -
5% Monolaurin Vaginal Gel

Note: Denominator for percentages is the number of subjects enrolled (N) in the study for each treatment group.

Tables with Similar Format:

Table 43: Nugent Scores by Category, Study Visit, Analysis Population, and Treatment Group - Placebo Gel

		5% Mon	olaurin Va (N=X)	ginal Gel]	Placebo Ge (N=X)	l	I	All Subject (N = X)	S
Analysis Population	Statistic	Visit 1 (N = X)	Visit 2 (N = X)	Visit 3 (N = X)	Visit 1 (N = X)	Visit 2 (N = X)	Visit 3 (N = X)	Visit 1 (N = X)	Visit 2 (N = X)	Visit 3 (N = X)
	Mean	x.xx	X.XX	X.XX	X.XX	X.XX	x.xx	X.XX	X.XX	X.XX
ITT	Standard Deviation of Mean	x.xx	x.xx	X.XX	X.XX	x.xx	X.XX	x.xx	x.xx	X.XX
111	Mean Change from Visit 1		x.xx	X.XX		X.XX	x.xx		X.XX	x.xx

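### The SAP plans no between-arm difference for the Nugent secondary outcome, and the Nugent table footnotes name an all-enrolled denominator that does not fit the mITT, Evaluable and PP rows

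*SAP*

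**What the plan says.** Protocol 11.7.2.1.1 lists among the secondary efficacy outcomes "Proportion of subjects with Nugent score of 3 or less (negative for BV) and 4-6 (intermediate) in each study arm at Visit 2", and the same at Visit 3. The secondary outcomes are to be analysed in the mITT population and again in PP, Evaluable and ITT. The reporting sentence is the same for primary and secondary outcomes: "The point estimates for the arm-specific proportions and difference in proportions as well as corresponding 95% confidence intervals will be reported".

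SAP 8.2 carries this out for clinical cure at Visit 3 and therapeutic cure at Visits 2 and 3, where it says "the difference in proportions between the 5% Monolaurin Vaginal Gel arm and the Placebo gel arm and 95% Wilson confidence intervals will be presented". For the Nugent categories it promises only this: "number and proportion of subjects with Nugent scores falling in negative, intermediate, and BV range is presented by analysis population, study visit, and treatment group", with Wilson intervals. Table 42 is the monolaurin shell and Table 43 the placebo shell; neither has a difference column.

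The Table 42 footnote, shared by Table 43 through its common format, is "Denominator for percentages is the number of subjects enrolled (N) in the study for each treatment group". Tables 38-41 carry the site version: "Denominator for percentages is the number of subjects enrolled (N) in the study for each Site". Each of these tables has rows for all four efficacy populations. The cure tables are worded differently: "The denominator for proportions is based on the number of subjects enrolled in the respective treatment group and analysis population".

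SAP Section 12 records a departure from the protocol on LOCF. It says nothing about the Nugent outcome.

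**The concern.** There are two separate faults in the same set of tables.

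- **Missing output.** The protocol asks for an estimated treatment difference with an interval on this outcome. The SAP delivers it for the other secondary outcomes but not for this one, and does not say that it was dropped.
- **Wrong denominator.** A footnote that divides every row by all enrolled subjects is right for ITT only. In the mITT, Evaluable and PP rows it counts people who are not in the population. Proportions come out too low and intervals are computed on too many subjects.

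The faults interact. A reader could rebuild the missing difference from the two single-arm tables, but would then inherit the footnote's denominator.

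**Working it through.** **Part 1: is the difference planned anywhere?**

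| Secondary outcome (Protocol 11.7.2.1.1) | SAP table | Difference and CI planned? |
|---|---|---|
| Clinical cure, Visit 3 | 30 | Yes |
| Therapeutic cure, Visits 2 and 3 | 31, 32 | Yes |
| Nugent 0-3 and 4-6, Visits 2 and 3 | 42, 43 | No |

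Table 44 (mean score and mean change) shows the arms side by side but has no difference column.

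**Part 2: size of the denominator effect**

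Inputs:
- Enrolment is 120 at 2:1, so 80/40 (Protocol 11.1, 11.5). SAP 6.6 says that the target was not raised after the interim look.
- The mITT goal is 90, split 60/30 (Protocol 11.5, Table 4).
- Event counts are my illustrative assumptions. The documents give none for Nugent categories.

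The plan states no figure for this outcome. As a check on the 60/30 sizes, I took one cell of the power table, monolaurin .50 against placebo .20. Exact enumeration of two-sided Fisher tests gives .783 against the stated .78.

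1. **Shrinkage factor.** Printed proportion = x/N_enrolled = (x/N_population) × (N_population/N_enrolled). For mITT the factor is 60/80 = 30/40 = .75.

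2. **Illustrative mITT row, with Wilson 95% intervals.**

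| | mITT denominator | Enrolled denominator |
|---|---|---|
| Monolaurin, 24 events | 24/60 = .40 (.286, .526) | 24/80 = .30 (.211, .408) |
| Placebo, 6 events | 6/30 = .20 (.095, .373) | 6/40 = .15 (.071, .291) |

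The monolaurin interval narrows from .526 − .286 = .240 to .408 − .211 = .197, with no added information.

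3. **What a reader would rebuild.** The SAP prints no difference, so this step is hypothetical. The Newcombe limits need only the printed proportions and Wilson limits: d − √[(p1 − l1)² + (u2 − p2)²] and d + √[(u1 − p1)² + (p2 − l2)²].
   - mITT denominators: .20 − √(.114² + .173²) = −.007 and .20 + √(.126² + .105²) = .364.
   - Enrolled denominators: .15 − √(.089² + .141²) = −.017 and .15 + √(.108² + .079²) = .284.

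4. **Consistency check.** The mITT population excludes a Visit 1 Nugent score below 4. With every score present, the Visit 1 categories 4-6 and 7-10 must sum to 1.00 in that population. Under the footnote they sum to about .75.

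5. **Unequal exclusions (assumed).** With mITT 56/34 of 80/40 and a true rate of .40 in both arms, the table prints .40 × 56/80 = .28 against .40 × 34/40 = .34, a gap of 6 points where there is none.

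6. **PP row (assumed).** If 50-70% of enrolled subjects qualify for PP, a true .50 prints as .25-.35.

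**The case against.** The strongest reply is that the footnote was carried over by accident and will not govern. The same sentence stands correctly under Table 34 (ITT), and its site version under Table 33 (all enrolled). SAP 8.2 says that results are given by analysis population. SAP 6.1 bases percentages on the sample size and displays the population size relevant to each table. The notes to Tables 55 and 56 use the word enrolled loosely, for membership of PP and mITT. The PROC FREQ code in SAP 6.1.1 uses whatever records it is fed, so the interval could come out on the right n even if the printed proportion did not. All of this stands, so understatement is conditional on literal programming and not certain. But the footnote is the only explicit denominator instruction in these shells, and it contradicts 8.2. Two programmers could produce different results. A proportion on 80 beside an interval on 60 (.30 with .286 to .526) would be no better.

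On the missing difference, SAP 6.1 and Section 8 say that intervals for differences in proportions will be computed for efficacy variables. That supplies a method but no table, whereas 8.2 names the output for the other secondary outcomes.

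Three stronger readings are tempting but not supported:
- A reader might infer that the Nugent objective gets no estimate at all. That objective is to evaluate changes in Nugent criteria, and unlike the other secondary objectives it does not name the placebo comparison. Table 44 gives mean change by arm in all four populations.
- A reader might infer that this is the only centrally read efficacy outcome. Therapeutic cure uses the same central Nugent score and has a difference with an interval; culture swabs also go to the central laboratory.
- A reader might infer that a hypothesis test was dropped. The protocol plans no p-value for any secondary efficacy outcome.

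**Conclusion.** The point holds in two parts.

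1. The difference in proportions with its 95% interval for Nugent 0-3 and 4-6, required by the protocol in four populations, has no planned output, and Section 12 does not declare the change. This rests on the text alone.
2. The footnotes of Tables 38-43 give a denominator that conflicts with SAP 8.2 and Tables 29-32. Tables 35-37 (Amsel criteria in mITT, Evaluable and PP) have the same fault if they carry over the Table 34 footnote. If programmed literally, mITT proportions shrink by 25%. That figure assumes the planned 60/30 of 80/40 and will move with the mITT fraction actually reached. The Evaluable and PP rows shrink at least as much when they hold no more subjects than mITT.

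The ITT row is right as it stands. The primary analysis (Table 29) and the therapeutic cure tables already use the population denominator, so a reader should not infer any effect on the main result. A literal misprint would also be visible, because counts are shown and Tables 3-4 give the population sizes. The plan should be corrected on both parts, but this is not a threat to the trial's principal conclusion.

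**What to change.** - In Tables 35-43, replace the denominator footnote with the wording of Tables 29-32: subjects in the respective treatment group (or site) and analysis population.
- Add one table in the Table 31 layout: active-minus-placebo difference with the Wilson/Newcombe 95% interval, for Nugent 0-3 and 4-6, at Visits 2 and 3, in ITT, mITT, Evaluable and PP. The SAP 6.1.1 code already covers the interval. Name the table in SAP 8.2.
- If the difference is deliberately not to be reported, say so in SAP Section 12 with the reason.

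The cost is footnote edits, one sentence in 8.2 and one extra table. No new data, test or multiplicity provision is involved.
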